7. PLANNED ANALYSIS

Descriptive data analysis of PK endpoints and plasma concentrations will be performed by [REDACTED] and monitored by the [REDACTED] [REDACTED] at BI and will be presented in Section 15.6 of the CTR and in Appendix 16.1.13.5.

For End-Of-Text tables, the set of summary statistics is: N / Mean / Standard deviation (StD) / Min / Median / Max. For tables that are provided for endpoints with some extreme data, median, quartiles and percentiles should be preferred to Mean, StD, Min and Max .

Tabulations of frequencies for categorical data will include all possible categories and will display the number of observations in a category as well as the percentage (%) relative to the respective treatment group (unless otherwise specified, all patients in the respective subject set whether they have non-missing values or not).

For plasma concentrations and PK parameters, the following descriptive statistics will additionally be calculated: number of observations (Nobs) / arithmetic coefficient of variation (CV) / geometric mean (gMean) / geometric coefficient of variation (gCV) / 10th percentile (P10) / 1st quartile (Q1) / 3rd quartile (Q3) / 90th percentile (P90).

The data format for descriptive statistics of plasma concentrations will be identical with the data format of the respective concentrations. The descriptive statistics of PK parameters will be calculated using the individual values with the number of decimal places as provided by the evaluation program. Then the individual values as well as the descriptive statistics will be reported with three significant digits in the CTR.

Sort order for general categorical variables: if categories correspond to the collected categories on the eCRF and the table shells do not explicitly specify the ordering, the “default ordering” defined by the eCRF is to be used in such cases. If categories are derived, the ordering as specified in the table shell document should be used; in general ordinal data (e.g., categorised continuous data) are to be displayed in ascending order. Abbreviations should not be displayed without any explanations. They will be either spelled out in the table or explained in footnotes (whatever is more reasonable from the programming point of view).

If applicable, conversion from days to weeks, months and years will be as follows:

- Weeks = Days / 7
- Months = (Days * 12) / 365.25
- Years = Days / 365.25

Exclusion of PK parameters

The ADS “ADPP” (PK parameters) contains column variables APEX and APEXCO indicating inclusion/exclusion (APEX) of a PK parameter and an analysis flag comment (APEXCO). All analyses based on the PKS will include parameters if they are not flagged for exclusion, that is APEX is equal to “Included”.

Exclusion of PK concentrations

The ADS “ADPC” (PK concentrations per time-point or per time-interval) contains column variables ACEX and ACEXCO indicating inclusion/exclusion (ACEX) of a concentration and an analysis flag comment (ACEXCO). Exclusion of a concentration depends on the analysis flag comment ACEXCO. For example, if ACEXCO is set to ‘ALL CALC’, the value will be excluded for all types of analyses based on concentrations. If ACEXCO is set to ‘DESC STATS’ the value will be excluded from descriptive evaluations per planned time point/time interval. If ACEXCO contains the addition ‘TIME VIOLATION’ or ‘TIME DEVIATION’ the value can be used for further analyses based on actual times. If ACEXCO is set to ‘HALF LIFE’, the value will be excluded from half-life calculation (and, as a consequence, any calculation that relies on λz) only; the value is included for all other analyses. Further details are given in BI-KMED-TMCP-MAN-0014 “Noncompartmental Pharmacokinetic / Pharmacodynamic Analyses of Clinical Studies” (6) and BI-KMEDTMCP-MAN-0010: “Description of Analytical Transfer Files and PK/PD Data Files” (7).

7.1 DEMOGRAPHIC AND OTHER BASELINE CHARACTERISTICS

Only standard descriptive statistics and summary tables are planned for this section of the report based on the treated set and other subject sets as appropriate. Data will be summarized by treatment group (i.e., dose cohort) and a “total” column will be included in the summary table.

Baseline demographics, oncological history, prior therapies, medical history, baseline eastern cooperative oncology group (ECOG) performance status, and baseline disease assessment are planned for this section.

7.2 CONCOMITANT DISEASES AND MEDICATION

Only descriptive statistics are planned for this section of the report based on the treated set and other subject sets as appropriate.

Concomitant diseases will be coded similarly as AEs based on the most current Medical Dictionary for Regulatory Activities (MedDRA) version. A summary of concomitant diseases will be provided by treatment group, system organ class (SOC), and preferred term (PT).

Concomitant therapies (CTs) will be coded according to World Health Organisation Drug Dictionary (WHO DD version: latest version before Data base lock). CTs will be classified according to the Anatomical Therapeutic Chemical (ATC) classification system. The third ATC level will be used to categorise CTs by therapy type. In situations where a medical product may be used for more than one equally important indication, there are often several classification alternatives. As appropriate, patients receiving CTs with more than one possible ATC level 3 category will be counted more than once. Footnotes will clarify this possible double counting in tables.

7.3 TREATMENT COMPLIANCE

Only descriptive statistics are planned for this section of the report.

7.4 PRIMARY ENDPOINT

7.4.1 Primary analysis of the primary endpoint

For the determination of the MTD, only evaluable patients for MTD in the dose escalation part will be considered (i.e., the MTD set). In this section of the report the data that led to the determination of the MTD are documented and summarised. To be specific, an overall summary of the number of patients with DLTs during the MTD evaluation period (i.e., the first treatment cycle) will be provided for each dose cohort.

The dose escalation and determination of MTD is guided by the BLRM with overdose control specified in CTP Section 7 based on the DLT data in the MTD set. Specifically, estimation of the MTD will be based on the estimation of the posterior probability of the incidence of DLT in toxicity categories during the MTD evaluation period for all evaluable patients for MTD. Tables and bar charts displaying the posterior probabilities of the true DLT rates being in either the under-toxicity interval, the target-toxicity interval or the over-toxicity interval will be produced.

7.5 SECONDARY ENDPOINTS

7.5.1 Key secondary endpoint

This section is not applicable as no key secondary endpoint has been specified in the protocol.

7.5.2 Secondary endpoints

The number of patients with DLTs during the on-treatment period at each dose level will be summarized in a frequency table.

The number of patients with CTCAE Grade ≥ 3 treatment-related adverse events observed during the on-treatment period at each dose level will be summarized in a frequency table (provided tables should be refer to [Section 7.8.1.2](#)).

The number of patients with treatment related adverse events at each dose level will be summarized in a frequency table.

The secondary PK endpoints (refer to [Section 5.2.2](#)) will be analysed descriptively. The analysis of standard PK parameters is calculated according to the relevant BI internal procedures “Noncompartmental Pharmacokinetic / Pharmacodynamic Analyses of Clinical Studies” (6).

7.7 EXTENT OF EXPOSURE

The total number of initiated cycles and treatment duration in days will be summarized descriptively for each dose cohort.

7.8 SAFETY ANALYSIS

All safety analyses will be performed on the treated set. Treated patients will be analyzed according to their initial treatment.

Patients who were replaced within the MTD evaluation period will be excluded from the determination of the MTD in the dose escalation but will be considered for all other safety evaluations.

Safety data recorded during the Residual Effect Period (REP) of 30 days will be considered as on-treatment.

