#### 2.1.3 Secondary endpoint(s)

- Number of patients with DLTs during the entire on-treatment period
- Number of patients with Grade  $\geq 3$  treatment-related adverse events
- Number of patients with treatment related adverse events at each dose level
- Pharmacokinetic parameters of BI 3011441:  $C_{max(ss)}$ , and  $AUC_{0-tz(ss)}$

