### 3. DESCRIPTION OF DESIGN AND TRIAL POPULATION

#### 3.1 OVERALL TRIAL DESIGN

The trial is an open-label, non-randomised phase I trial of BI 3011441 as monotherapy to investigate the safety/tolerability, PD and PK profile at selected dose levels in Japanese patients with NRAS/KRAS mutation positive advanced or metastatic refractory solid tumours. Patients will be enrolled based on the available NRAS/KRAS mutation status previously identified by local test results performed prior to screening. The data obtained from the trial will determine the MTD estimate based on a Bayesian logistic regression model with overdose control ([R13-4803](#)). The BLRM estimates the MTD by updating estimates of the probability of observing a DLT in the MTD evaluation period for each dose level in the trial as patient information becomes available. At any time in the trial, it will not be permitted to escalate to a dose which does not fulfil the escalation with overdose control (EWOC) principle (refer to [Section 7](#)).

The provisional dose levels to be evaluated will be 4mg, 6mg and 8mg, which includes the previously established MTD of 8mg for Caucasian patients. For any dose-escalation cohort, at least 3 patients will be required (refer to Section 7). However, in the case that only 2 patients are evaluable and neither has experienced a DLT within the MTD evaluation period, then dose-escalation can occur based on these 2 patients. For determination of MTD or RD, 6 patients will be enrolled at least. A BLRM with overdose control will be performed once the enrolment of 3 patients at each dose level has been completed and these patients completed the first cycle of treatment of BI 3011441. Each cycle will consist of 28 days (4 weeks) and patients will continue the treatment until undue drug toxicity, disease progression, or withdrawal of consent, whichever occurs first. The longest treatment period will be 2 years if deemed safe and efficacious. Intra-patient dose escalation will be allowed if there is an indication from higher-dose cohorts that there is a positive-risk-benefit once the patient completed the 1st cycle of treatment including PK sampling.

[figure not shown]

Figure 3.1: 1

Study design

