#### 4.1.4.2 Dose reductions and dose delays

For the assessment of the severity of adverse events (AEs), CTCAE version 5 ([R18-1357](#)) will be used. Any SAEs/AEs of  $\geq$ Grade 2 deemed intolerable by the patient or the treating physician and not responding to appropriate medical management, and any related SAEs/AEs of  $\geq$ Grade 3 will result in the interruption of treatment with BI 3011441 until resolution to baseline or Grade 1. Please see [section 3.3.4.1](#) for the permanent IMP discontinuation criteria.

Proprietary confidential information © 2020 Boehringer Ingelheim International GmbH or one or more of its affiliated companies

If the treatment interruption is  $\leq 2$  weeks, the patient can be re-exposed to BI 3011441 at the same dose or one dose level lower than the dose administered before the interruption as long as the re-exposure is considered clinically indicated by the Investigator. However, dose reduction is not allowed for patient who uses 4 mg, and the study medication (BI 3011441) needs to be discontinued.

In case the treatment is delayed due to an AE, the patient should visit the site at least once a week for assessment of safety laboratory and AEs. More frequent visits may be appropriate as assessed by the Investigator. Any case of a delay in treatment cycle for more than 2 weeks should be communicated to the Sponsor. The Investigator in agreement with the Sponsor will decide about further treatment of individual patient, based on known risk/benefit of BI 3011441.

A maximum of 1 dose reductions of BI 3011441 are allowed, if lower tested dose levels are available. Dose reductions will be only to doses previously explored in earlier cohorts.

In case of dose reductions, all future dose administrations will also be at the reduced dose level. If that is intolerable (as previously described), the treatment of that patient should be discontinued. Recommendations for dose reductions of BI 3011441 are given in [Tables 4.1.4.2: 1, 4.1.4.2: 2, and 4.1.4.2: 3](#).

Proprietary confidential information © 2020 Boehringer Ingelheim International GmbH or one or more of its affiliated companies

Table 4.1.4.2: 1

Dose modification for BI 3011441 for haematologic and non-haematologic toxicity related to treatment

Haematologic and non-haematologic toxicity	Dose modification
Grade 1	

Continue BI 3011441 at full dose, monitor as clinically indicated.

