7.8.1 Adverse Events

Statistical analysis and reporting of adverse events will concentrate on treatment-emergent adverse events, i.e., all adverse events occurring between start of treatment and end of the REP. All adverse events will be evaluated by initial treatment.

Frequency, severity, and causal relationship of adverse events will be tabulated by system organ class and preferred term after coding according to the current version of the Medical Dictionary for Drug Regulatory Activities (MedDRA) at database lock.

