7.8.1.1 Maximum tolerated dose and dose limiting toxicity

For the determination of MTD in this trial, the following will be evaluated:

- Posterior distribution is based on the number of patients with DLTs with regard to the MTD set and DLTs occurring during the MTD evaluation period (i.e., the first treatment cycle in dose escalation). The toxicity rates for the respective toxicity intervals will be evaluated.
- A table displaying DLTs by primary system organ class and preferred term will be provided by initial treatment for the MTD evaluation period for the MTD Set as well

as for the treated set. The same table will additionally be displayed for all treatment cycles of the on-treatment period for the treated set.

- The purpose of these tables is to summarize and document the data that led to the selection of MTD. A summary of the number of patients with DLT within the MTD evaluation period and for all treatment cycles of the on-treatment period will be given by initial treatment for the treated set.

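### All-cycle DLTs and adverse events are tabulated by starting dose although a patient's dose can change, so the by-dose safety tables can show an event under a dose no longer being taken

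*SAP*

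**What the plan says.** **Dose can change within a patient.** Protocol 3.1: "Intra-patient dose escalation will be allowed if there is an indication from higher-dose cohorts that there is a positive-risk-benefit", and this applies "once the patient completed the 1st cycle of treatment including PK sampling". Protocol 4.1.4.2 allows one reduction: "In case of dose reductions, all future dose administrations will also be at the reduced dose level".

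**Endpoints and analyses are by dose.** Protocol 2.1.3 lists "Number of patients with treatment related adverse events at each dose level". Protocol 7.3.3 plans the on-treatment DLT table by dose level. SAP 7.5.2 does so for on-treatment DLTs, related Grade 3 or higher AEs and related AEs.

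**Attribution is to the starting dose.** SAP 7.8: "Treated patients will be analyzed according to their initial treatment". SAP 7.8.1: "All adverse events will be evaluated by initial treatment". SAP 7.8.1.1 says that the DLT summary "for all treatment cycles of the on-treatment period will be given by initial treatment for the treated set".

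**Nothing in the visible text offsets this.** SAP 6.1 defines one on-treatment block, from first dose to last dose plus 30 days, with no split by dose received. SAP 7.7 summarises exposure by dose cohort only. There is no dose-at-onset rule, no display of patients who changed dose, and no cut-off at the change.

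**The concern.** A table with a row per dose is read as what happened at that dose. Under the SAP rule, a 4 mg starter who moves to 8 mg and then has a DLT is reported in the 4 mg row. An 8 mg starter who is reduced and then has an event stays in the 8 mg row. This follows from a stated rule, not from a gap in the text.

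The later-cycle data matter. Protocol 5.2.6.3 says that events meeting the DLT criteria in any cycle are considered for the recommended dose, and Protocol 2.1.1 plans a BLRM rerun with all DLTs at the end of escalation as one input to it. Protocol 1.3 also stresses understanding safety at the lower doses, and those are the rows that receive events from escalated patients. With about 12 patients in all, one event changes a row visibly.

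**Working it through.** **1. Which data are exposed.** Escalation within a patient is possible only after Cycle 1. The MTD evaluation period is Cycle 1 (Protocol 2.1.1), and a Cycle 1 reduction for a related AE is itself a DLT (Protocol 5.2.6.3). The main MTD analysis is therefore essentially untouched. The marginal exception is a DLT found at the Cycle 2 Day 1 eye or echocardiography assessment, which also counts for the MTD. What is exposed is the data from Cycle 2 on.

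**2. Size in a table.** One event moves a 3-patient row from 0/3 = 0% to 1/3 = 33%.

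**3. Size in the BLRM rerun, if starting dose were used there.** Model (Protocol 7.1): logit(π_d) = log α + β·log(d/8), with the three-component prior of Table 7.1:2, integrated on a grid. Overdose means π_d ≥ 0.33, and the limit is 25%.

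Reproduction of the protocol's own overdose probabilities:

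| Case | Protocol | Grid |
|---|---|---|
| Prior, 4 / 6 / 7 / 8 mg | 0.128 / 0.233 / 0.310 / 0.422 | 0.129 / 0.232 / 0.310 / 0.422 |
| Scenario 1, 4 mg | 0.026 | 0.026 |
| Scenario 2, 4 mg | 0.194 | 0.206 |
| Scenario 20, 8 mg | 0.106 | 0.103 |
| Scenario 21, 8 mg | 0.274 | 0.268 |

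The largest difference is 0.012.

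Assumed data: one 4 mg starter escalates to 8 mg and has a later DLT there. Cycle 1 gave 0/3 at 4 mg, 0/3 at 6 mg, and either 1/6 (case A) or 2/6 (case B) at 8 mg.

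| Case and assignment | 4 / 6 / 8 mg | Mean DLT rate, 4 mg | P(overdose) 4 mg | 7 mg | 8 mg |
|---|---|---|---|---|---|
| A, starting dose | 1/3, 0/3, 1/6 | 0.118 | 0.017 | 0.113 | 0.199 |
| A, dose at onset, patient in both rows | 0/3, 0/3, 2/7 | 0.058 | 0.004 | 0.058 | 0.212 |
| A, dose at onset, patient once | 0/2, 0/3, 2/7 | 0.063 | 0.006 | 0.067 | 0.219 |
| B, starting dose | 1/3, 0/3, 2/6 | 0.149 | 0.046 | 0.257 | 0.396 |
| B, dose at onset, patient in both rows | 0/3, 0/3, 3/7 | 0.069 | 0.010 | 0.144 | 0.422 |
| B, dose at onset, patient once | 0/2, 0/3, 3/7 | 0.077 | 0.015 | 0.162 | 0.432 |

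In case A the estimated 4 mg rate about doubles (0.118/0.058 = 2.0), but no dose crosses 25%. In case B the assignment alone moves 7 mg across 25%. That crossing is narrow: 0.257 exceeds the limit by 0.007, less than the largest reproduction difference. The gap between assignments, 0.257 − 0.144 = 0.113, is well outside it.

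**The case against.** **Cohort reading.** Protocol 4.1.2 assigns dose levels to separate cohorts, and SAP 7.1 equates treatment group with dose cohort. Summaries by starting dose are a legitimate cohort description. This stands, and is a reason to keep those tables. They do not by themselves show what happened at each dose once doses change.

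**The safety committee sees the patients.** Under Protocol 4.1.2 it reviews each patient in the current cohort in detail and discusses later-cycle data on ongoing patients. The trial is open and the CRF records dose. With about 12 patients, dose at onset can be recovered. A reader might infer that the recommended dose rests on the starting-dose tables; the documents do not support that. The problem is in what is tabulated and reported.

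**Dose at onset has faults of its own.** It can credit cumulative or delayed toxicity to the latest dose, and escalated patients are selected for having tolerated a lower one. Entering one patient at two doses in a model of DLT within the MTD evaluation period is debatable. All of this stands, so such tables should supplement and not replace.

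**Limited visibility.** Parts of the SAP are blacked out, and the table shells and sponsor AE standards are not available here. A supplementary display may exist there. The rule in the visible text is nevertheless explicit.

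**Conclusion.** The point holds for the all-cycle by-dose tables. Whenever a patient changes dose, the SAP's rule can report an event under a dose that patient was no longer taking, at a size of up to 0/3 versus 1/3 per event in a small cohort. It rests on at least one patient changing dose and then having an event; the documents give no expected frequency.

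Three stronger readings are not supported:

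- A reader might infer that low-dose toxicity is systematically overstated and the dose-toxicity curve flattened. Reductions push the other way, so the net direction is unknown.
- A reader might infer that the BLRM rerun is distorted. The SAP's BLRM text (7.4.1, 7.8.1.1) covers Cycle 1 DLTs in the MTD set, and no text assigns a dose to later-cycle DLTs in the rerun. The effect is conditional and depends on the data, as cases A and B show.
- A reader might take Scenarios 1 and 2 of Table 10.2:1 (0.026 versus 0.194 at 4 mg) as the size of the effect. Those scenarios hold 4 mg data only. The rerun comes at the end of escalation, and a patient can escalate only on evidence from higher-dose cohorts, so higher-dose data must exist. In case A the corresponding figures are 0.017 by starting dose and 0.004 by dose at onset.

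**What to change.** Keep the starting-dose cohort tables as they are. Then:

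1. In SAP 7.5.2 and 7.8.1.1, add supplementary tables of all-cycle DLTs, related AEs and related Grade 3 or higher AEs by dose at onset, defined as the last dose taken before onset. Use patients exposed and patient-cycles at each dose as denominators.
2. List every patient who changed dose, with the date and direction of change and any later events.
3. For the all-DLT BLRM rerun of Protocol 2.1.1, state which dose a later-cycle DLT is assigned to, and show the result under both assignments as a sensitivity analysis. State how the denominators are formed. This does not require entering one patient at two doses.

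The cost is SAP wording, a few tables and one listing, with no change to trial conduct. A patient may appear in more than one dose column. A footnote should say so, and should also note the cumulative-toxicity and selection caveats. The tables by dose at onset stay supplementary.

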7.8.1 Adverse Events

Statistical analysis and reporting of adverse events will concentrate on treatment-emergent adverse events, i.e., all adverse events occurring between start of treatment and end of the REP. All adverse events will be evaluated by initial treatment.

Frequency, severity, and causal relationship of adverse events will be tabulated by system organ class and preferred term after coding according to the current version of the Medical Dictionary for Drug Regulatory Activities (MedDRA) at database lock.

7.8.1.1 Maximum tolerated dose and dose limiting toxicity

For the determination of MTD in this trial, the following will be evaluated:

- Posterior distribution is based on the number of patients with DLTs with regard to the MTD set and DLTs occurring during the MTD evaluation period (i.e., the first treatment cycle in dose escalation). The toxicity rates for the respective toxicity intervals will be evaluated.
- A table displaying DLTs by primary system organ class and preferred term will be provided by initial treatment for the MTD evaluation period for the MTD Set as well

as for the treated set. The same table will additionally be displayed for all treatment cycles of the on-treatment period for the treated set.

- The purpose of these tables is to summarize and document the data that led to the selection of MTD. A summary of the number of patients with DLT within the MTD evaluation period and for all treatment cycles of the on-treatment period will be given by initial treatment for the treated set.

